### 6.1.1.3 Monitoring of Dose Administration

Participants will be monitored during administration of [In]-FPI-2107, FPI-2053, or [Ac]-FPI-2068, and for 30 minutes after administration for each cycle. Participants will then be monitored as clinically indicated thereafter. Vital signs and electrocardiogram (ECG) will be measured according to the schedules described in Section 8.4.2 and Section 8.4.3, respectively. In the event of an infusion-related reaction (IRR), see [Table 15](#) for the TMGs and retreatment criteria.

As with any biologics product, allergic reactions to dose administration are possible. Therefore, appropriate drugs and medical equipment to treat acute anaphylactic reactions must be immediately available, and study personnel must be trained to recognise and treat anaphylaxis.

## 6.1.2 Non-investigational Products

### 6.1.2.1 Premedication for IRR

No premedication for the prevention of IRR prior to the first administration of [Ac]-FPI-2068, [In]-FPI-2107 or FPI-2053 is permitted (i.e., primary prophylaxis). Any planned premedication with acetaminophen (paracetamol), histamine (H1 and H2)-receptor antagonists, with subsequent administrations of [Ac]-FPI-2068, [In]-FPI-2107 or FPI-2053 following an IRR (i.e., secondary prophylaxis) is permitted. Steroids should not be used as routine premedication for Grade 1 or 2 IRRs. If more than 1 participant during the course of the study develops a Grade  $\geq 3$  IRR during the first infusion, the SRC may recommend premedication for all subsequent participants to be implemented for the first infusion as follows: paracetamol/acetaminophen (500 to 1000 mg orally) and diphenhydramine (25 to 50 mg orally or IV; or an alternative antihistamine at an adequate dose), should be administered approximately 30 minutes prior to administration of [Ac]-FPI-2068, [In]-FPI-2107 or FPI-2053. H2-receptor antagonists (e.g., ranitidine) may be added if clinically indicated.

## 6.2 Preparation/Handling/Storage/Accountability

- The Investigator or designee must confirm appropriate temperature conditions have been maintained during transit for all study interventions received and any discrepancies are reported and resolved before use of the study intervention.
- Only participants enrolled in the study may receive study interventions and only authorised site staff may supply or administer study interventions. All study interventions must be stored in a secure, environmentally controlled, and monitored (manual or automated) area in accordance with the labelled storage conditions with access limited to the Investigator and authorised site staff.

- The Investigator, institution, or the head of the medical institution (where applicable) is responsible for study intervention accountability, reconciliation, and record maintenance (i.e., receipt, reconciliation, and final disposition records).
- Accountability, reconciliation, and destruction of the study intervention will be conducted in accordance with the relevant site SOPs. Unused study intervention is to be destroyed at the exhaustion, expiry, or end of study usage.
- Further guidance and information for the final disposition of unused study interventions are provided in the Pharmacy Manual.

### **6.2.1      Investigational Medicinal Products Receipt, Handling, and Storage**

The Investigator is responsible for ensuring that the IMPs (FPI-2053, [In]-FPI-2107, and [Ac]-FPI-2068) are correctly received, handled, stored, used, and disposed of in accordance with regulatory guidelines, the CSP, the IB, and the Pharmacy Manual.

### **6.2.2      Participant Protection**

All handling of radiopharmaceuticals must be carried out in restricted areas by persons trained and authorised in the safe use, handling, and administration of radiopharmaceuticals to humans. Care must be taken to minimise contamination of clothing and skin of personnel with the use of disposable gloves and protective clothing. Hands must be washed after handling any radioactive materials. All handling of radioactive material must follow site Standard Operating Procedures and the regulations and radionuclide licenses issued by the local nuclear regulatory authorities. Before, during, and after administration of [In]-FPI-2107 and [Ac]-FPI-2068, sites should follow the regulations set forth by the competent nuclear regulatory agency with jurisdiction over the site.

The participant and caregivers will be given instructions regarding hygiene precautions after receiving the drug to minimise risk of potential radiation exposure of the 3rd party.

For further information refer to the Pharmacy Manual.

### **6.3          Dose Calibration Setting**

Reference standards will be supplied to allow each site to calibrate equipment including dose calibrators for indium-111 and actinium-225 prior to the first participant enrolment as detailed in the Site Imaging Manual.

### **6.4          Measures to Minimise Bias: Randomisation and Blinding**

This is an open-label, non-randomised study; no blinding is required. Participants will be allocated to Part A Cohorts 1 or 2 in an alternating manner.

### **6.5          Study Intervention Compliance**

Participants are to receive IMP in accordance with the dose range specified in the CSP. If a

participant received a dose outside the specified range, the Investigator should contact the Sponsor and/or Medical Monitor immediately, monitor the participant for any TEAE/SAE(s), and document the event in the eCRF.

The administration of all study intervention should be recorded in the appropriate sections of the eCRF. Any changes from the dosing schedule, dose interruptions, dose reductions, and dose discontinuations should be recorded in the eCRF. The reason should also be documented.

Use of doses in excess of that specified in the CSP is considered to be an overdose. Refer to Section 8.6 for procedures in case of overdose.

When participants are dosed at the site, they will receive study intervention directly from the Investigator or designee, under medical supervision. The date, and time if applicable, of dose administered in the clinic will be recorded in the source documents and recorded in the eCRF. The dose of study intervention and study participant identification will be confirmed at the time of dosing by a member of the study site staff other than the person administering the study intervention.

## 6.6 Concomitant Therapy

All concurrent medical conditions and complications of the underlying malignancy will be treated at the discretion of the Investigator according to standard of care and institutional practice guidelines and procedures. If there is a clinical indication for any medication or vaccination specifically prohibited during the study, discontinuation from study treatment may be required.

Participants should receive analgesics, antiemetics, antibiotics, antipyretics, and blood products, as necessary. Any medication, including vaccines, over-the-counter or prescription medicines, vitamins, and/or herbal supplements that the participant received within 30 days prior to signing informed consent or receives during the study must be recorded including reason for use, dates of administration including start and end dates, and dosage information including dose and frequency.

Concomitant medications will be collected according to the timepoints outlined in the SoAs (see Section 8.1). If a participant is currently receiving bisphosphonates for treatment of osteoporosis, treatment-induced bone loss, or metastases to bone, the participant must have started treatment with the bisphosphonates at least 4 weeks prior to the first dose of study treatment.

The IMP excretion is partially hepatic; it is at the Investigator's discretion to treat participants with laxatives to accelerate excretion from the intestine.

Prior and concomitant therapies will be coded using WHO Drug Version 01 March 2022 or higher.

Any medication or vaccine (including over-the-counter or prescription medicines, vitamins, and/or herbal supplements) that the participant is receiving at the time of enrolment or

receives during the study must be recorded along with:

- Reason for use
- Dates of administration including start and end dates
- Dosage information including dose and frequency

The Study Physician should be contacted if there are any questions regarding concomitant or prior therapy.

Participants must abstain from taking prescription or non-prescription drugs (including vitamins and dietary or herbal supplements) within 7 days (or 14 days if the drug is a potential enzyme inducer) or 5 half-lives (whichever is longer) before the start of study intervention until completion of the follow-up visit, unless, in the opinion of the Investigator, Medical Monitor, and Sponsor, the medication will not interfere with the study.

Acetaminophen, at doses of  $\leq$  2 g/day, is permitted for use at any time during the study. Other concomitant medication may be considered on a case-by-case basis by the Investigator in consultation with the Sponsor and Medical Monitor if required.

### 6.6.1 Prohibited Treatment

The following treatments are not allowed during the study treatment and for 28 days post last dose of study intervention:

- Any concurrent anticancer therapy, including but not limited to, chemotherapy, radiotherapy, hormonal therapy, immunotherapy, or locoregional therapy
- Immunosuppressive therapies, including continuous high-dose corticosteroids (except when used: intermittently in an antiemetic regimen; for the management of study intervention-related adverse events; in participants with contrast allergies; or for CNS metastases management), methotrexate, azathioprine, and tumour necrosis factor- $\alpha$  blockers. Use of inhaled, topical, and intranasal corticosteroids is permitted.
- Any vaccine within 30 days prior to the first dose of FPI-2053 or [In]-FPI-2107 (see Exclusion Criterion 12 in Section 5)
  - Killed, viral vector, and mRNA vaccines may be allowed after completion of the DLT-period upon agreement between the Investigator, Sponsor, and Medical Monitor.
- Live or attenuated vaccines are prohibited
- Other investigational agents for any disease indication
- Herbal and natural remedies which may have immune-modulating effects.

### 6.6.2 Medications to be Used with Caution

The potential of [Ac]-FPI-2068 to be associated with drug-drug interactions has not been established. It is anticipated that the major route of excretion will be via the kidneys; therefore, medications which might affect renal function should be avoided or used with caution as assessed by the Investigator. These medications include but are not limited to the following:

Drugs causing prerenal damage:

- Drugs that cause excessive gastrointestinal losses, either through diarrhoea or vomiting, also cause volume depletion and may precipitate acute kidney injury (AKI).
- Nonsteroidal anti-inflammatory drugs (NSAIDs), even in short courses, can cause AKI as a result of renal under perfusion.
- Angiotensin-converting enzyme (ACE) inhibitors can also cause a deterioration in renal function. However, this is concerning only in participants with compromised renal perfusion, particularly those with renal artery stenosis.
- Care should be taken when an ACE inhibitor and NSAID are prescribed together, as this combination may precipitate an acute deterioration in renal function.

Drugs causing intrarenal damage:

- Intrarenal damage may result in a direct toxic effect on the kidneys or hypersensitivity reactions.
- Most drugs that cause damage within the kidneys do so as a result of hypersensitivity reactions, which involve either glomerular or interstitial damage.
- Drugs that have been reported to cause glomerulonephritis include penicillamine, gold, captopril, phenytoin, and some antibiotics, including penicillins, sulfonamides, and rifampicin.
- Drugs that may cause interstitial nephritis include penicillins, cephalosporins, sulfonamides, thiazide diuretics, furosemide, NSAIDs, and rifampicin.
- There are several drugs that cause direct toxicity to the renal tubules (acute tubular necrosis); e.g., aminoglycosides, amphotericin, and ciclosporin.

Drugs causing postrenal damage (urinary tract obstruction):

- High-dose sulfonamides, acetazolamide or methotrexate may cause crystalluria and could therefore cause urinary tract obstruction.
- Anticholinergics (e.g., tricyclic antidepressants) and alcohol may cause urinary tract obstruction due to retention of urine in the bladder.

Other nephrotoxic drugs:

- Cephalosporins: cephaloridine, one of the first cephalosporins introduced, has been associated with direct renal toxicity and is no longer in clinical use. Other cephalosporins are much less likely to produce renal damage but third generation cephalosporins (e.g., cefixime) have (very rarely) been reported to cause nephrotoxicity.

Analgesics:

- NSAIDs may cause AKI due to hypoperfusion and interstitial nephritis, as well as analgesic nephropathy (chronic interstitial nephritis and papillary necrosis).
- Analgesic nephropathy has been most seen with combination analgesic products that contain aspirin and/or paracetamol.

## **6.7 Dose Modification**

### **6.7.1 [In]-FPI-2107**

The [In]-FPI-2107 185 MBq (5 mCi) dose will not be modified during the study.

### **6.7.2 FPI-2053**

Intraparticipant dose modifications for FPI-2053 will not occur during the study.

### **6.7.3 [Ac]-FPI-2068**

For a participant to be eligible to receive repeat dosing with [Ac]-FPI-2068, they must meet the retreatment criteria defined in [Table 15](#) within 56 days (+ 4 weeks) from their previous [Ac]-FPI-2068 administration. If retreatment criteria are not met, the treatment administration may be held for up to 28 days. If treatment-related toxicities are not resolved within this window, then the participant will discontinue study treatment. Adjustments to these guidelines may occur if agreed by the Investigator, Sponsor, and Medical Monitor.

**Table 15      Toxicity Management Guidelines and Retreatment Criteria**

Event	Characteristic	Grade	Management recommendation
Anaemia, leucopenia, or neutropenia	Haemoglobin $\leq$ 9g/dL WBC $< 3 \times 10^9/L$ ANC $< 1.5 \times 10^9/L$	$\geq 2$	Hold [  Ac]-FPI-2068 (with or without FPI-2053) until improvement to Grade 1 or baseline. Dose may be held for up to 4 weeks beyond the next planned dose per CSP (i.e., beyond 56 days). Manage as deemed appropriate by Investigator. Use of growth factors is permitted but should be discontinued once the AE resolves to Grade 1 or baseline. Transfusions may be given as clinically indicated for anaemia.
Thrombocytopenia	Platelets: $> 50 \times 10^9/L$ and $< 75 \times 10^9/L$	2	Hold [  Ac]-FPI-2068 (with or without FPI-2053) until improvement to Grade 1 or baseline, retreat at the same dose level. Manage as deemed appropriate by Investigator. Transfusions may be given as clinically indicated for thrombocytopenia.
	Platelets: $< 50 \times 10^9/L$	3 and 4	Hold [  Ac]-FPI-2068 (with or without FPI-2053) until improvement to Grade 1 or baseline, reduce by one dose level. Manage as deemed appropriate by Investigator. Transfusions may be given as clinically indicated for thrombocytopenia.
Increased serum creatinine	CrCl 30-59 mL/min/1.73 m 	2	Hold [  Ac]-FPI-2068 (with or without FPI-2053) until improvement to Grade 1 or baseline. If resolved in $\leq 7$ days, then maintain dose level for the next cycle. If resolved in $> 7$ days, then reduce by one dose level for the next cycle. Manage as deemed appropriate by Investigator.
	CrCl 15-29 mL/min/1.73 m 	3	Treatment should be permanently discontinued.

Event	Characteristic	Grade	Management recommendation
	CrCl < 15-29 mL/min/1.73 m  ; dialysis or renal transplant indicated	4	Treatment should be permanently discontinued.
Increased AST or ALT	> 5.0 - 20 x ULN if baseline was normal; > 5.0 baseline if baseline was abnormal	3	Hold [  Ac]-FPI-2068 (with or without FPI-2053) until improvement to Grade 1 or baseline or ≤ Grade 2 if liver metastases are present. If resolved in ≤ 7 days, then maintain dose level for the next cycle. If resolved in > 7 days, then reduce by one dose level for the next cycle.
	> 20.0 × ULN if baseline was normal; > 20.0 × baseline if baseline was abnormal	4	Treatment should be permanently discontinued.
Increased total bilirubin	> 3.0 - 10.0 × ULN if baseline was normal; > 3.0 - 10.0 × baseline if baseline was abnormal	3	Hold [  Ac]-FPI-2068 (with or without FPI-2053) until improvement to Grade 1 or baseline. If resolved in ≤ 7 days, then reduce by one dose level for the next cycle. If resolved in > 7 days, then permanently discontinue study drug
	> 10.0 × ULN if baseline was normal; > 10.0 × baseline if baseline was abnormal	4	Treatment should be permanently discontinued.
Non-haematologic AEs		3	Hold [  Ac]-FPI-2068 (with or without FPI-2053) until improvement to Grade 1 or baseline. If resolved < 7 days, then maintain dose level for the next cycle. If resolved > 7 days, then reduce by one dose level for the next

Event	Characteristic	Grade	Management recommendation
			cycle.
		4	Treatment should be permanently discontinued.
Infusion-related reaction		1	
The infusion rate may be decreased by 50% or temporarily interrupted until resolution of the event.
 
Monitor closely and manage per institutional standard at the discretion of Investigator.
 
If no other reactions appear, the subsequent infusion rate could be resumed at the initial planned rate.

		2	
Temporarily interrupt study intervention administration.
 
If the event resolves or improves, infusion can be restarted at a 50% reduced infusion rate.
 
Consider discontinuation if recurrent Grade 2 despite premedication and 50% reduced infusion rate.
 
Acetaminophen and/or antihistamines may be administered per institutional standard at the discretion of the Investigator.
 
Steroids should not be used for routine premedication of Grade <math>\leq 2</math> infusion-related reactions.
 
Consider appropriate premedication prior to subsequent doses (see Section 6.1.2).

		3-4	
Discontinue study intervention.
 
Manage severe infusion-related reactions per institutional standards (e.g., IM epinephrine, followed by IV diphenhydramine and famotidine, and IV glucocorticoid IV fluid therapy, oxygen inhalation etc).

ILD/pneumonitis		Any grade	
Please follow the dose modifications specific to each severity grade.
 
Closely monitor participants for signs and symptoms of pneumonitis or ILD (e.g., new onset or worsening shortness of

Event	Characteristic	Grade	Management recommendation
			
breath or cough).
 
Consider the following to exclude alternative aetiologies:
 
 
• Chest CT (preferably high resolution CT) and pulmonologist consultation as clinically indicated
 
• Chest X-ray
 
• Pulmonary function tests (spirometry, DLCO)
 
• Physical examination
 
• Monitor oxygen saturation via pulse oximetry
 
• Laboratory work-up as indicated
 

		1	
Note: if participants remain asymptomatic, then the event should be considered as Grade 1, even if treatment with corticosteroids is given.
 
Hold all study intervention for 21 days, immediately upon detection.
 
If pulmonary function tests at 21 days after Grade 1 pneumonitis/ILD detection are not showing clinically meaningful deterioration and in the absence of symptoms and stable SpO2, all study intervention can be resumed at the same dose level.
 
Repeat spirometry and DLCO after 21 days from detection.
 
Consider additional imaging (e.g., HRCT scan) if feasible.
 
Monitor for symptoms onset and oxygen saturation as clinically indicated.
 
Consider starting systemic corticosteroids per institutional guidelines.
 
If symptoms appear follow Grade 2 guidelines.

		2	
Permanently discontinue study intervention.
 
Promptly start and treat with systemic steroids per institutional guidelines.

Event	Characteristic	Grade	Management recommendation
		3-4	Monitor symptoms closely. Re-image as clinically indicated. Consider additional work-up for alternative aetiologies as described above. Escalate care as clinically indicated.
			Permanently discontinue study intervention. Hospitalisation required. Promptly initiate high-dose corticosteroids treatment per institutional guidelines. Re-image as clinically indicated. Consider additional work-up for alternative aetiologies as described above. Consider other immunosuppressants (e.g., infliximab or mycophenolate) per local practice.
Radiation dose estimates	Planned activity does not exceed cumulative limits of 23 Gy for kidneys, 31 Gy for liver, 16.5 Gy for lungs, and for Part A only, 2 Gy for red bone marrow.	NA	Dosimetry estimate of the previously administered and planned cumulative administered activity of [  Ac]-FPI-2068 (with or without FPI-2053), based on individual uptake as assessed by [  In]-FPI-2107 imaging (with or without FPI-2053). Additionally, the absorbed radiation dose to the kidney, liver, and lung from prior EBRT treatment must be taken into account and considered part of the cumulative dose to the organs when determining the number of cycles of treatment that a participant can receive. If a planned dose level may exceed the total allowable cumulative dose, the participant may receive a reduced administration such that the specified cumulative limit is not reached.

AE, adverse event; ALT, alanine aminotransferase; ANC, absolute neutrophil count; AST, aspartate aminotransferase; CrCl, creatinine clearance; CT, computed tomography; DLCO, diffusing capacity of the lungs for carbon monoxide; EBRT, external beam radiation therapy; HRCT, high resolution computed tomography; ILD, interstitial lung disease; IM, intramuscular(ly); IV, intravenous(ly); NA, not applicable; SpO2, pulse oximetry; ULN, upper limit of normal; WBC, white blood cell count.

If moderate or severe AEs are consistently observed across participants in a cohort or if unacceptable pharmacological effects, reasonably attributable to study intervention in the opinion of the Investigator are observed in more than 30% of the participants in a cohort, then dose escalation will be temporarily halted and no further participants will be dosed until a full safety review of the study has taken place by the SRC. Relevant reporting and discussion with the Study Physician, relevant site personnel, and the Institutional Review Board (IRB)/Independent Ethics Committee (IEC) will take place before resumption of dosing.

The above criteria will apply even if measured PK parameters are below the prespecified PK stopping criteria, and every effort will be made to take a blood sample at the time of the AE for PK analysis.

In case a dose reduction is necessary, the study intervention will be administered as outlined in [Table 15](#).

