##### [Ac]-FPI-2068

For Part A (first radiation dose level, 15 kBq/kg with and without unlabelled bsAb), dosimetry estimates of all previous and planned therapeutic administrations of [Ac]-FPI-2068 do not exceed a cumulative exposure of 23 Gy for kidneys, 31 Gy for liver, 2 Gy for red bone marrow, and 16.5 Gy for lungs. Additionally, the absorbed radiation dose to the kidneys, liver, and lungs from prior EBRT treatment must be taken into account and considered part of the cumulative dose to the organs when determining the number of cycles of treatment that a participant can receive. Eligible participants will receive up to 3 cycles of [Ac]-FPI-2068.

For Part B, dosimetry estimates of all previous and planned therapeutic administrations of [Ac]-FPI-2068 do not exceed a cumulative exposure of 23 Gy for kidneys, 31 Gy for liver, and 16.5 Gy for lungs. The absorbed radiation dose to the kidneys, liver, and lungs from prior EBRT treatment must be taken into account and considered part of the cumulative dose to the organs when determining the number of cycles of treatment that a participant can receive.

Eligible participants will receive up to 3 cycles of [Ac]-FPI-2068.

If a planned dose level exceeds the total allowable cumulative dose, the participant may receive a reduced dose.

The dose level of [Ac]-FPI-2068 will be determined by the assigned dose level (see [Table 7](#) and [Table 8](#)).

The volume to be administered to a given participant should be calculated using the:

- participant's body weight (kg)
- dosage level (in kBq/kg body weight)
- radioactivity concentration of the product at time of calibration (the activity concentration at time of calibration and the date of calibration are provided on the vial and lead pig label)

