**Table 13** **Investigational Products**

Intervention name	[  In]-FPI-2107	FPI-2053	[  Ac]-FPI-2068
Type	Biologic	Biologic	Biologic
Dose formulation	Solution for injection	Concentrate for infusion	Solution for injection
Unit dose strength(s)	74–111 MBq/mL (at time of calibration)	100 mg/vial	0.407–0.629 MBq/mL (at time of calibration)
Dosage level(s)	185 MBq (5 mCi) a, b	Proposed 0.3, 1, and 3 mg/kg Q8W c	Proposed 15, 25, 40, and 70 kBq/kg Q8W b
Route of administration	IV injection	IV infusion	IV injection
Use	Experimental	Experimental	Experimental
IMP or NIMP	IMP	IMP	IMP
Sourcing	Provided centrally by the Sponsor	Provided centrally by the Sponsor	Provided centrally by the Sponsor
Packaging and labelling	Study intervention will be labelled in accordance with GMP Annex 13 and per country regulatory requirement	Study intervention will be labelled in accordance with GMP Annex 13 and per country regulatory requirement	Study intervention will be labelled in accordance with GMP Annex 13 and per country regulatory requirement
Aliases	None	None	None

GMP, Good Manufacturing Practice; IMP, investigational medicinal product; IND, investigational new drug; IV, intravenous; NIMP, non-IMP; Q8W, every 8 weeks.

a [In]-FPI-2107 is only given during the imaging screening period. All participants will receive 2 doses of [In]-FPI-2107 unless the optimal dose of FPI-2053 from Part A is 0, in which case participants in Part B will receive one dose.

b Administered dose tolerances for [In]-FPI-2107 and [Ac]-FPI-2068 are outlined in the Pharmacy Manual.

c The proposed FPI-2053 dose levels of 0.3, 1, and 3 mg/kg will be used in Part A. The FPI-2053 dose level in Part B will be determined in Part A.

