#### **6.7.4 Starting Dose, Dose Escalation Scheme, and Stopping Criteria**

Part A Cohort 1 and Cohort 2 will be initiated simultaneously and enrol in parallel.

Participants will be assigned in an alternating manner. The first participant in Cohort A2 will be treated with [Ac]-FPI-2068 only after the first participant in Cohort A1 has undergone a minimum of one week of safety observation. Dosing of [Ac]-FPI-2068 in Part A will be 15 kBq/kg/cycle and be administered at this dose for up to a maximum of 3 cycles. If FPI-2053 is to be administered prior to [Ac]-FPI-2068 or FPI-2107 then the interval between the administration of FPI-2053 and FPI-2068 or [In]-FPI-2107 will be 30 minutes to 2 hours. Following review of safety, PK, biodistribution, and dosimetry data from Cohorts A1 and A2 by the Sponsor and the SRC, Cohort A3 may be initiated if deemed necessary.

In Part B there will be a minimum of 56 days between completion of dosing in the last evaluable participant, for a dose escalation decision, from one cohort and the start of dosing in the subsequent cohort.

There may be ongoing participants who become evaluable after the dose escalation decision (i.e., dosing may start in the next cohort whilst these participants are ongoing).

Intra-participant dose escalation is not permitted.

The dose for subsequent cohorts or a decision to stop recruitment will be agreed by the SRC after review of the data from each cohort (see Section [6.7.8](#)).

In Part B a minimum of three and a maximum of nine participants will be enrolled at a given dose level.

Part B, dose escalation to the next dose level will be conducted using the mTPI-2 algorithm with a target DLT rate of 30% and an equivalence interval (25%, 35%). A minimum of 3 participants must complete the DLT-evaluation period before making an escalation decision. Dose escalation will consist of four planned dose levels. Intermediate dose levels may be

explored if warranted by emerging safety, PK, pharmacodynamic, biomarker, and efficacy data. Dose escalation and de-escalation will follow the mTPI-2 algorithm schema below:

- A minimum of 3 evaluable participants are required in each dose level unless unacceptable toxicity is encountered in the first 2 subjects prior to enrolment of the third participant, which would require dose de-escalation per the mTPI-2 design.

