## **7 DISCONTINUATION OF STUDY INTERVENTION AND PARTICIPANT DISCONTINUATION/WITHDRAWAL**

### **7.1 Discontinuation of Study Intervention**

It may be necessary for a participant to permanently discontinue (definitive discontinuation) study intervention prior to completion of the Treatment Period. If study intervention is permanently discontinued, the participant will remain in the study to be evaluated for follow-up- assessments. See the SoA for the End of Treatment and Extended Follow-up period (see [Table 25](#)) for data to be collected at the time of discontinuation of study intervention and follow-up, and for any further evaluations that need to be completed.

Note that discontinuation from study intervention is NOT the same as withdrawal from the study (see Section [7.1.1](#)).

The participant should continue attending subsequent study visits and data collection should continue according to the CSP. If the participant does not agree to continue in-person study visits, a modified follow-up must be arranged to ensure the collection of endpoints and safety information. This could be a telephone contact with the participant at the Extended Safety Follow-up visit, a contact with a relative or treating physician, or information from medical records. The approach taken should be recorded in the medical records. A participant who agrees to modified follow-up is not considered to have withdrawn consent or to have withdrawn from the study.

Participants will continue to receive repeat cycles of treatment at the dose level and schedule of administration at which they were enrolled:

- up to a maximum of three cycles or
- until individual participant-specific cumulative radiation dose limits to specified organs based on [In]-FPI-2107 imaging are reached (see Section [4.3](#)).

Participants must also be discontinued from study treatment in the following situations:

- Unacceptable AE or inability to tolerate study therapy
- Delay in dosing of 28 days, without approval of Sponsor or Medical Monitor

- Documented, confirmed radiographic progressive disease (PD) (as assessed per RECIST 1.1)
  - Participants may remain on study treatment following confirmed radiographic PD if, in the opinion of the Investigator and with the agreement of the Sponsor and/or Medical Monitor, they continue to derive clinical benefit from the study treatment and if the following criteria are met:

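### Table 15 calls for retreatment one dose level lower, but no level exists below 15 kBq/kg and no default is set for participants already there

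*Protocol*

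**What the plan says.** Section 6.7.3 makes the retreatment criteria in Table 15 a condition of repeat dosing. Within the table, Grade 3-4 thrombocytopenia leads to a hold "until improvement to Grade 1 or baseline, reduce by one dose level". For Grade 3 bilirubin the text is "If resolved in ≤ 7 days, then reduce by one dose level for the next cycle". Three more rows ask for the same one-level step when the event takes more than 7 days to resolve: Grade 2 creatinine, Grade 3 AST or ALT, and other Grade 3 non-haematologic events.

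Table 13 gives the [225Ac]-FPI-2068 levels as "Proposed 15, 25, 40, and 70 kBq/kg Q8W". Section 6.1.1.2 confirms which is lowest: "For Part A (first radiation dose level, 15 kBq/kg with and without unlabelled bsAb". Tables 7 and 8 place all of Part A, and Part B Cohort 0, at 15 kBq/kg. The predose offers no alternative step, because Section 6.7.2 states "Intraparticipant dose modifications for FPI-2053 will not occur during the study".

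The text after Table 15 points back to the table: "In case a dose reduction is necessary, the study intervention will be administered as outlined in" Table 15. Section 6.7.9 does the same. Section 6.7.4 says dosing "in Part A will be 15 kBq/kg/cycle and be administered at this dose for up to a maximum of 3 cycles". Section 7.1 says "Participants will continue to receive repeat cycles of treatment at the dose level and schedule of administration at which they were enrolled".

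**The concern.** A one-level reduction is the protective step that Table 15 attaches to retreatment after these toxicities. At 15 kBq/kg there is nothing to step down to, and the protocol does not say whether such a participant stops, is retreated at 15 kBq/kg, or receives some smaller activity.

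The matter is participant safety in Cycles 2 and 3 of a first-in-human alpha emitter. The thrombocytopenia row shows it best. Section 6.7.7.1 counts Grade 4 thrombocytopenia of any duration as a DLT, yet Table 15 does not end treatment for it. It allows another cycle after recovery, at a lower level. At the starting dose that added protection is empty, and the only dose sentences that still name an amount or a level are the unqualified ones in Sections 6.7.4 and 7.1.

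**Working it through.** The check is mainly a comparison of texts, with some simple counting.

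**1. Is there a level below 15 kBq/kg?** The defined levels (Tables 7, 8 and 13) are 15, 25, 40 and 70 kBq/kg. The minimum is 15, so no defined level lies below it. The 10 kBq/kg dose appears only in the version history, as superseded text.

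**2. Which rows use the instruction?** Five in Table 15:
- thrombocytopenia, Grade 3-4;
- creatinine, Grade 2, resolving in more than 7 days;
- AST or ALT, Grade 3, resolving in more than 7 days;
- bilirubin, Grade 3, resolving in 7 days or less;
- other non-haematologic events, Grade 3, resolving in more than 7 days.

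**3. Which starting levels run out?** With at most 3 cycles there can be at most 3 - 1 = 2 reductions. On the planned levels:
- 70 to 40 to 25: defined;
- 40 to 25 to 15: defined;
- 25 to 15 to none: second step undefined;
- 15 to none: first step undefined.

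Two of the four planned levels are therefore affected.

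**4. Does other text supply the missing dose?**
- The smaller activities in Sections 4.3.3, 6.1.1.2 and 8.3 are computed from cumulative organ dose limits. They give no amount for a reduction prompted by observed toxicity.
- The Safety Review Committee may explore alternative or intermediate levels (Section 6.7.8). That is a cohort decision, and nothing below 15 kBq/kg is named.
- Section 6.7.3 allows adjustments by three-party agreement but states no action in its absence.
- The mandatory stop for an unacceptable adverse event in Section 7.1 does not settle the case, because Table 15 treats these recovered events as retreatable.

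**5. What does the literal text leave?** A specific toxicity rule would ordinarily qualify a general schedule sentence. At 15 kBq/kg the specific rule yields no dose, so what remains is 15 kBq/kg per cycle (Section 6.7.4, Part A) or the enrolled level (Section 7.1, all parts).

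**6. How many are exposed?** Inputs are three participants per Part A cohort, two or three cohorts, and three to nine participants per Part B level.
- Part A: 2 x 3 = 6 without Cohort A3; 3 x 3 = 9 with it (Section 4.1 estimates 9).
- Cohort 0 of Part B: 0 if not opened, otherwise 3 to 9.
- Total: 6 + 0 = 6 up to 9 + 9 = 18.

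Replacements, de-escalation to 15 kBq/kg and backfill are not counted and could add more.

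**The case against.** The strongest reply is that the event is not left unmanaged. Table 15 is headed as guidelines, its column gives recommendations, and the thrombocytopenia row leaves management to the Investigator. Section 6.5 requires dosing within the protocol's dose range, Section 8 forbids waivers, and Section 6.7.3 makes any adjustment depend on the Investigator, Sponsor and Medical Monitor together. Section 8 also sends immediate safety concerns to the Medical Monitor or Sponsor. A site can always stop a participant on its own decision (Section 7.1).

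Much of this stands. A reader might infer that different sites could each improvise a smaller activity and cite the protocol for it. The documents do not support that: an activity below 15 kBq/kg that is not a dosimetry adjustment needs central agreement, and one Sponsor serves all sites. It is also fair that retreatment after a DLT-level event is a separate criticism, applying at every dose level and not a measure of this gap.

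What does not stand is the inference that nothing needs to be written. Central agreement says who may decide, not what happens by default. Retreating at 15 kBq/kg accords with the dose sentences in Sections 6.7.4 and 7.1 read literally, so a site could see it as no departure at all.

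**Conclusion.** The gap is real and should be closed in the next amendment. Five Table 15 rows prescribe a step with no target at 15 kBq/kg (first reduction) or 25 kBq/kg (second reduction), no default fills it, and two unqualified dose sentences point towards full-dose retreatment.

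Its size is bounded. The 6 to 18 participants are those treated at 15 kBq/kg, not those harmed or even affected. To be affected, a participant must meet one of the five rows, recover within the allowed window and otherwise qualify for another cycle. The protocol gives no rate for that and none is assumed here. The 25 kBq/kg case needs two qualifying events within three cycles and assumes the planned levels, with no intermediate level added.

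A reader might also infer that dose-finding is compromised. It is not: DLTs are counted in Cycle 1 only (Section 6.7.7), so the mTPI-2 decisions and the MTD are unchanged.

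**What to change.** Add a footnote to Table 15: a participant already at the lowest defined [225Ac]-FPI-2068 level who meets a row calling for a one-level reduction discontinues [225Ac]-FPI-2068 by default, unless a level -1 activity in kBq/kg has been defined, or the Investigator, Sponsor and Medical Monitor agree otherwise under Section 6.7.3.

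Add *unless reduced or discontinued per Table 15* to the dose sentences in Sections 6.7.4 and 7.1.

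The cost is one footnote and two short insertions. The downside is that a few recovered participants may lose later cycles. That could include some with a Grade 3 non-haematologic event lasting more than 7 days that was not related to treatment, since that row is not limited to related events. The agreement clause and the option of a level -1 keep room for such cases.
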